7.0 SAFETY ANALYSES

7.1 Physical Examination

The study clinician will complete a physical examination, including blood pressure and heart rate, to ensure that there are no medical concerns regarding participation and to gather baseline information regarding the participant's physical health. During the screening physical exam, a description of the participant's body habitus will be documented and the study clinician will examine the planned injection sites to ensure adequacy for XR-NTX gluteal intramuscular injection of naltrexone with the supplied needle. The physical examination will be performed at screening and will be repeated at the end-of-medication visit (if medication is stopped early) or at the end-of-treatment visit (week 24). The physical exam, blood pressure and/or heart rate may be repeated at MM visits at the discretion of the medical clinician.

7.2 Concise Health Risk Tracking-Self Report (CHRT-SR)

The CHRT-SR (Trivedi 2011) is a 16-item participant self-report assessment of suicidality and related thoughts and behaviors. The scale is designed to quickly and easily track suicidality in a manner consistent with the Columbia Classification Algorithm of Suicide Assessment (C-CASA) S (Posner 2007). The CHRT-SR will be assessed at screening, induction, at subsequent MM visits and at the week 28 and 36/EOS visits. The CHRT-SR will assess high risk suicide ideation by a positive response (Agree or Strongly Agree) on any of the last three questions (thoughts of, thoughts of how and/or a specific plan to commit suicide) and prompt a clinician assessment for suicide risk before leaving the clinic.

7.3 The Hamilton Depression Scale (17 item) (HAM-D)

The 17-item Hamilton Depression Scale (HAM-D) is a clinician-administered instrument, useful for following both depression and suicidal ideation, and also for following typical symptoms of subacute withdrawal (e.g., low appetite, fatigue, poor sleep). For the purpose of this study, adequately trained research staff conduct the Hamilton Depression Scale (HAM-D).

The HAM-D is completed at screening, at weeks 1, 2, 3, 4, 8, 12, 16 and 20, at the end-of-treatment visit (week 24/EOT), and at each follow-up. A score of 1 or more to item 3 (suicidality) prompts a clinician assessment for suicide risk before leaving the clinic. Summaries of the suicidality question are tabulated for the purposes of safety analyses.

The HAM-D score is calculated by summing the first 17 items on the HAM-D form. A sum of 0 to 7 is considered to be normal, 8 to 13 is defined as mild depression, 14 to 18 as moderate depression, 19 to 22 as severe depression, and greater than or equal to 23 is defined as very severe depression.

7.4 Clinical Laboratory Tests

Liver function tests (LFTs, consisting of AST, ALT, albumin and bilirubin) and urine pregnancy test (for females) will be performed to help determine eligibility at screening. Receipt and review of laboratory test results is necessary before confirming eligibility, conducting randomization and starting study medication. Results of LFTs conducted within four weeks prior to randomization (e.g., collected as part of routine detoxification admission) will be acceptable. For participants whose induction onto their assigned study medication is delayed for longer than 2 weeks after randomization, LFTs and urine pregnancy should be repeated prior to start of study medication.

At screening, blood will be collected for HIV antibody, hepatitis C virus (HCV) antibody and hepatitis B surface antigen (HBsAG) and hepatitis B surface antibody (HBsAB) tests. These tests do not determine eligibility and will only be conducted on samples from participants who are randomized. Results of HIV antibody, hepatitis C virus (HCV) antibody and hepatitis B surface antigen (HBsAG) and hepatitis B surface antibody (HBsAB) tests conducted within four

weeks prior to randomization (e.g., collected as part of routine detoxification admission) will be acceptable.

For participants whose induction onto their assigned study medication occurs within 2 weeks of Day 0, LFTs will be repeated at week 4, week 12, and at the end-of-medication visit (if medication is stopped early) or at the end-of-treatment visit (week 24). For participants whose induction onto their assigned study medication occurs more than 2 weeks after day 0, LFTs will be repeated approximately 4 and 12 weeks following induction (a +/- 2 week window for post-induction LFTs is permitted), and at the end-of-medication visit (if medication is stopped early) or at the end-of-treatment visit (week 24). For participants who do not get inducted but continue on study, LFTs need not to be repeated at any of the planned visits with scheduled LFTs.

A laboratory that is accredited by the College of American Pathologists (CAP) or equivalent, and participates in the Clinical Laboratory Improvement Act of 1998 (CLIA) will perform these analyses. The laboratory will provide normal values and proof of lab certifications.

Changes in the liver function test values (alkaline phosphatase, ALT, AST, GGT and total bilirubin) over time and by treatment arm will be considered graphically. A listing of participants with elevated AST and ALT by treatment arm will be presented.

7.4.1 Adverse Events (AEs) and Serious Adverse Events (SAEs)

At each medical management visit the study clinician will assess for AEs and SAEs by asking the study participant, "How have you been feeling since your last visit?" AEs and SAEs may also be spontaneously reported to study staff at any visit following consent. AEs and SAEs suggesting medical or psychiatric deterioration will be brought to the attention of a study clinician for further evaluation and management. Medical management visits will emphasize overdose risk and risk-management; any reported overdose will be recorded as an AE or SAE. AE and SAE reporting will be according to the reporting definitions and procedures outlined in the protocol and in accordance with applicable regulatory requirements.

For the purpose of this study, the following AE will not require reporting in the data system but will be captured in the source documentation as medically indicated:

- Grade 1 (mild) unrelated adverse events

This would typically include mild physical events such as headache, cold, etc., that were considered not reasonably associated with the use of the study drug/intervention.

Events related to the injection of the study medication will be recorded on the Injection Site Abnormality (INA) form and will not be duplicate-reported on an AE form (See Section 7.4 for details on Injection Site examination summaries). Events related to withdrawal symptoms will be captured on the SOWS and HAM-D and will not be duplicate-reported on an AE form. Withdrawal symptoms not captured by the SOWS or HAM-D should be reported as an AE. Events captured on study specific forms (INA, SOWS, HAM-D) will not be recorded separately as an AE, unless they meet the SAE definition. Any of these events that meet the definition of an SAE will be reported on the AE/SAE form set. Any spontaneous reporting of withdrawal symptoms by the participant will be captured on AE form in the following situations: withdrawal symptoms reported at visits without scheduled specific structured questionnaires (SOWS, HAM-D); and withdrawal symptoms not listed in the specific structured questionnaires (SOWS, HAM-D) reported at any visit.

Adverse events (AEs), including serious adverse events (SAEs), will be summarized by body system and preferred term using MedDRA (The Medical Dictionary for Regulatory Activities) version 19.0 or higher. Adverse events will be presented in two ways: (1) the number and proportion of participants experiencing at least one incidence of each event will be presented overall and by treatment group. The incidence of adverse events and serious adverse events by

type will be compared between treatment arms using either Fisher's Exact mid-p-value or Chi-Square analysis as appropriate; and (2) a table displaying the total number of each event will be given overall and by treatment group. Listings of serious adverse events will be given, sorted by treatment, body system and preferred term. Detail in these listings will include severity, relationship to study drug, and action taken as available.

Treatment emergent AEs are defined as AEs occurring after participants have been inducted on study medication. Induction is defined as having had an injection if in the XR-NTX arm or having been dispensed medication if in the BUP-NX arm.

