11.2.7 Adverse Events (AEs) and Serious Adverse Events (SAEs)

At each medical management visit the study clinician assesses for AEs and SAEs by asking the study participant, "How have you been feeling since your last visit?" AEs and SAEs may also be spontaneously reported to study staff at any visit following consent. AEs and SAEs suggesting medical or psychiatric deterioration will be brought to the attention of a study clinician for further evaluation and management. Medical management visits will emphasize overdose risk and risk-management; any reported overdose is recorded as an AE or SAE. AE and SAE reporting is according to the reporting definitions and procedures outlined in the protocol and in accordance with applicable regulatory requirements.

For the purpose of this study, the following AEs do not require reporting in the data system but is captured in the source documentation as medically indicated:

- Grade 1 (mild) unrelated adverse events

This would typically include mild physical events such as headache, cold, etc., that were considered not reasonably associated with the use of the study drug/intervention.

Events related to the injection of the study medication are recorded on the Injection Site Abnormality (INA) form and will not be duplicate-reported on an AE form. Events related to withdrawal symptoms are captured on the SOWS and HAM-D and will not be duplicate-reported on an AE form. Withdrawal symptoms not captured by the SOWS or HAM-D should be reported as an AE. Events captured on study specific forms (INA, SOWS, HAM-D) are not recorded separately as an AE, unless they meet the SAE definition. Any of these events that meet the definition of an SAE are reported on the AE/SAE form set. Any spontaneous reporting of withdrawal symptoms by the participant are captured on AE form in the following situations: withdrawal symptoms reported at visits without scheduled specific structured questionnaires (SOWS, HAM-D); and withdrawal symptoms not listed in the specific structured questionnaires (SOWS, HAM-D) reported at any visit.

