1.5 Randomization

Immediately following the final assessment of eligibility, participants will be randomly assigned to one of the two conditions: XR-NTX or BUP-NX. Random assignment will be on a 1:1 ratio to one of the two conditions. A restricted randomization plan will be used with centralized, automated, randomized block assignments. Randomization will be stratified by two factors, site and pre-detoxification level of opioid use. While there will be important and otherwise uncharacterized differences between sites – including state and local treatment service environments, opioid misuse epidemiology, and patient-level customs regarding treatment, medications, and clinical trial participation – the level of heroin and other opioid use will likely be an important independent predictor of treatment retention and rates of negative urines as has been demonstrated in recent analysis of naltrexone opioid trials (Sullivan et al 2006; Carpenter et al 2009; Brooks et al 2010). The level of opioid use at treatment entry is a binary classification, operationally defined as 6 or more bags (or equivalent) IV heroin per day (≥ 6 bags/day) over the 7 days prior to entry into the treatment program versus less than 6 bags (or equivalent) IV heroin per day (< 6 bags/day) or other routes of administration or other opioids.

Eligible participants will be randomized in a 1:1 ratio to the BUP-NX and XR-NTX arms. The randomization process will be performed by computer at a centralized location. Randomization will be stratified by site and pre-detoxification level of opioid use [≥ 6 or more bags (or equivalent) IV heroin per day (≥ 6 bags/day) over the 7 days prior to entry into the treatment program versus less than 6 bags (or equivalent) IV heroin per day (< 6 bags/day) or other routes of administration or other opioids]. The block size chosen will be adequate to ensure approximate treatment balance. The number in each treatment group will never differ by more than a factor of $KB/2$ where B is the block size and K is the number of strata.

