2.2 Secondary Outcomes

Table 1: Protocol Secondary Outcomes and Hypotheses	
Outcomes	Hypotheses
Proportion successfully inducted onto assigned study medication (binary: did or did not receive first dose of XR-NTX, or achieve maintenance dose of BUP-NX)	BUP-NX will produce higher rate of successful induction than XR-NTX Significance/Rationale: XR-NTX induction requires completion of detoxification, whereas BUP-NX induction only requires onset of withdrawal symptoms. Thus XR-NTX may have more dropouts after randomization but prior to XR-NTX induction.
Adverse Events related to study medications	XR-NTX and BUP-NX will produce equivalent rates of SAEs, and equivalent rates of AEs, though AE pattern will differ somewhat (e.g. injection site reactions with XR-NTX) Significance/Rationale: Careful documentation of SAEs and AEs, including overdose episodes, would be considered essential safety data, and important component of a comparative effectiveness trial.
Opioid abstinence over time while on study medication (Weekly TLFB, confirmed by urine drug screens)	XR-NTX will produce greater opioid abstinence than BUP-NX Significance/Rationale: XR-NTX produces complete blockade of opioid effects, so that during treatment with monthly injections, opioid use can be expected to be minimal. In contrast BUP-NX may not produce complete blockade, or patients may reduce or stop doses for a few days and substitute other opioids (heroin, prescription opioids).

Table 1: Protocol Secondary Outcomes and Hypotheses	
Outcomes	Hypotheses
Alcohol and other drug use, over time (TLFB and UDS)	
XR-NTX will be superior to BUP-NX in producing abstinence from alcohol and other drugs
 
Significance/Rationale: Clinical trials show XR-NTX is effective for treatment of alcohol dependence, and naltrexone has some evidence of efficacy for stimulant dependence.

Cigarette smoking (FTND, Tobacco Use Questionnaire, VAS nicotine craving)	
XR-NTX will reduce cigarette smoking compared to BUP-NX
 
Significance/Rationale: Naltrexone has been studied as a treatment for nicotine dependence, with some support from clinical trials, although inconsistent. Given high morbidity and mortality associated with nicotine dependence, a comparative advantage of one or the other of these treatments at reducing smoking would be valuable to examine.

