3.5 Software

All analyses will be performed utilizing SAS® version 9.3. All statistical tests will be conducted at the 5% Type I error rate (two-sided). When multiple tests are conducted, the chance of finding a significant difference in one of the tests, when in fact no difference exists, is greater than the stated Type I error rate. The investigators are aware of the multiple testing issues and will interpret results with caution and use confidence intervals where possible.

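### The by-arm AE totals leave out non-serious injection-site reactions, so they can undercount XR-NTX while BUP-NX oral reactions are counted

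*SAP*

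**What the plan says.** **Recording.** Under SAP 7.4.1, injection-related events "will be recorded on the Injection Site Abnormality (INA) form and will not be duplicate-reported on an AE form". The exception follows in the same section: "Any of these events that meet the definition of an SAE will be reported on the AE/SAE form set". Protocol 11.2.7 agrees that events captured on the study-specific forms "are not recorded separately as an AE, unless they meet the SAE definition"; protocol 13.6.4 and Appendix A repeat the rule.

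**Hypothesis.** In SAP Table 1 (section 2.2) the outcome is AEs related to study medication. The expectation is "equivalent rates of AEs, though AE pattern will differ somewhat (e.g. injection site reactions with XR-NTX").

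**Comparison.** SAP 7.4.1 plans that AE and SAE incidence by "type will be compared between treatment arms using either" Fisher's exact "mid-p-value or Chi-Square analysis as appropriate". No equivalence margin is stated.

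**Reporting.** The Table 33 shell gives, by arm, participants with a treatment-emergent AE, number of events, severity and relatedness. Table 35 gives an any-AE row and MedDRA terms by arm. Injection-site abnormalities appear in Table 45 (count, type and severity by site, with a Total column) and in the listing in Table 46. SAP 7.5 describes the site examination and promises the listing.

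**The concern.** Only XR-NTX participants receive study injections, so the recording rule removes events from one arm. The other arm's local effects stay in: the Table 35 shell carries glossitis, glossodynia, oral mucosal erythema and oral discomfort. Mild events show the asymmetry most clearly. Only Grade 1 *unrelated* AEs are exempt from data entry, so a mild oral reaction judged related to BUP-NX is entered as an AE, while a mild injection-site reaction to XR-NTX is not.

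The outcome is defined as AEs related to study medication, so the relatedness row of Table 33 is the closest match to the hypothesis, and it is among the rows affected. If those rows look similar between arms, they may be read as support for equal AE rates, although the event that the hypothesis names was never in the count.

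Table 45 does not let a reader repair this. It is not cross-classified with AE-form events, so the number of participants with any AE, injection-site events included, cannot be worked out. Its stated denominator is participants randomized to XR-NTX, whereas Tables 33 and 35 cover events after induction.

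**Working it through.** The plan gives no expected rate, margin or power for the AE comparison, so there is no planned figure to reproduce. The direction follows from the rule alone. The size can only be illustrated.

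**Inputs**
- *p*, the share of each arm with at least one AE on the AE form: not stated. Assumed equal in both arms, 30% to 70%.
- *q*, the share of XR-NTX participants with an injection-site reaction: not stated for this trial. The label in protocol Appendix C gives, for 380 mg in alcohol-dependence trials, any reaction 142/205 = 69.3% (placebo injection 106/214 = 49.5%) and injection-site pain 34/205 = 16.6%. In its placebo-controlled opioid trial, injection-site pain was 6/126 = 4.8%. I use 5%, 17% and 69%, with 30% as an assumed middle value.
- Test level: "All statistical tests will be conducted at the 5% Type I error rate (two-sided"). Allocation is 1:1 (SAP 1.5), with about 600 randomized, so about 300 per arm. The number inducted, which is the relevant denominator, is not given and cannot exceed this.

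**Formula.** If reactions are independent of other AEs, the XR-NTX any-AE rate with reactions counted is 1 − (1 − p)(1 − q). The omitted difference is this minus p, which equals (1 − p)q.

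For p = 50%: 0.50 × 0.05 = 0.025; 0.50 × 0.17 = 0.085; 0.50 × 0.30 = 0.15; 0.50 × 0.69 = 0.345.

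| q | Omitted difference, p = 30% | p = 50% | p = 70% | Power at p = 50%, 300 per arm |
|---|---|---|---|---|
| 5% | 3.5 points | 2.5 | 1.5 | 9% |
| 17% | 11.9 | 8.5 | 5.1 | 55% |
| 30% (assumed) | 21.0 | 15.0 | 9.0 | 96% |
| 69% | 48.3 | 34.5 | 20.7 | about 100% |

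**Without independence.** If every reaction falls in someone who already has an AE on the form, the difference in participants with any AE is 0, although event totals still fall short. If none does, the difference is the smaller of q and 1 − p. At p = 50% that is 5, 17, 30 and 50 points for the four values of q.

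**The reverse case.** Suppose the true any-AE rates, reactions included, were equal at 50%, with q = 17%. The AE form would then show 1 − 0.50/0.83 = 39.8% on XR-NTX against 50% on BUP-NX. At 300 per arm, a two-sided 5% test of that row would have about a 71% chance of a significant difference favouring XR-NTX.

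**Rows affected.** The undercount can enter the any-AE, related, severity and event-total rows of Tables 33 and 35. Rows for other event types do not depend on where injection-site reactions are recorded. Serious injection-site events are on the AE/SAE forms, so Tables 34 and 36 are unaffected.

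**The case against.** The strongest reply is that the reactions are reported, and in detail. SAP 7.5 has the site examined at the next medical management visit after the injection. Table 45 gives participants, events, type and severity, and its Total column is the XR-NTX figure. A BUP-NX column would be zero by design. The hypothesis can also be read as a carve-out: it expects injection-site reactions to differ, so comparing the remaining AEs and showing these apart fits its wording. This stands as far as it goes. The data are not lost, and separate presentation is legitimate. It does not supply a combined any-AE figure or tell a reader of Tables 33 and 35 what is missing.

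A second reply is that pooling has its own imbalance. Injection sites are actively examined, while other AEs, oral reactions included, come from an open question or spontaneous report. A combined row may therefore lean against XR-NTX. This stands too, and is why the combined row should sit beside the AE-form-only row and not replace it.

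A third is that the planned test is by event type, so the SAP does not clearly plan a test of the any-AE row. This also stands. The power figures describe a test that an analyst might run on that row, not one that the SAP specifies.

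A reader might also infer that withdrawal symptoms are excluded in the same one-sided way. The documents do not support that. The exclusion applies to both arms, has exceptions for symptoms not on the questionnaires and visits without them, and the scores are tabulated by arm in Tables 25, 26 and 47. It could lean the same way, since SAP Table 1 expects worse first-month withdrawal symptoms on XR-NTX, but that is a possibility only.

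**Conclusion.** The point holds for the summary rows. Non-serious injection-site reactions are outside the by-arm any-AE, related, severity and event-total rows, nothing planned puts them back, and BUP-NX oral reactions are inside. The omission can lower the XR-NTX figures and cannot raise them. A statement of equivalent AE rates resting on those rows would leave out the one example that the hypothesis gives.

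Three stronger readings are tempting and not supported:
- That the whole AE comparison is biased. Other event-type rows and the SAE comparison are not affected.
- That all injection-site reactions are kept out of the AE tables. Serious ones are entered, and the Table 35 shell carries an injection site abscess term, although that may be only an example.
- That a difference of 15 to 35 points is hidden. This needs a 50% AE-form rate, independence, and reaction rates of 30% (assumed) to 69% (alcohol-dependence trials, with 50% on placebo injections).

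The size cannot be obtained from the documents. Under independence it runs from 1.5 to about 48 points over the ranges shown, and it is zero for participants with any AE under complete overlap. The 5% figure is for pain alone, and the label rates are not restricted to non-serious reactions, so neither end is an estimate for this trial.

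**What to change.** Leave data collection unchanged. Then:

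1. Add by-arm rows to Tables 33 and 35 for any AE including injection-site form events, covering participants with any event, related, severity and event total, beside the AE-form-only rows. Code the abnormality types to MedDRA injection-site terms and treat them as related, since the form is for injection-related events.
2. Use the same post-induction population for both sets of rows. State how reactions on the day of the first injection are handled, because the table footnotes count only events after the study day of induction.
3. Report the arm comparison both ways, noting that injection sites are actively examined and that the combined row may therefore lean against XR-NTX.
4. Footnote that the AE-form rows exclude non-serious injection-site events (shown in Tables 45 and 46) and withdrawal symptoms captured on the SOWS and HAM-D (Tables 25, 26 and 47). Limit any equivalence statement to the events counted.
5. Correct the cross-reference in SAP 7.4.1, which sends the reader to 7.4 for injection-site summaries that are in 7.5.

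The cost is coding terms already collected, a few table rows and two footnotes. No new data are needed.

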11.4.6 The Subjective Opioid Withdrawal Scale (SOWS)

This scale is useful for following self-reported opioid withdrawal symptoms. It is administered at baseline, induction, weekly during the first month after randomization, and at weeks 8, 12, 16, and 20, at the end of treatment (EOT/week 24), and at each follow-up. At the induction visit for the XR-NTX group the SOWS is administered three times, the first time within the hour prior to the naloxone challenge, the second time 10-30 minutes following the naloxone challenge, and the third time 1-3 hours following the XR-NTX injection. At the induction visit for the BUP-NX group, the SOWS is administered twice, the first time within the hour prior to BUP-NX dosing and the second time 1-3 hours following dosing.

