Opioid Craving (VAS) over time	
XR-NTX will be superior to BUP-NX in reducing opioid craving
 
Significance/Rationale: Krupitsky et al (Lancet 2011) pivotal XR-NTX trial showed, surprisingly, that XR-NTX reduced craving substantially compared to placebo.

Subacute withdrawal symptoms over time (HAM-D, SOWS)	
XR-NTX will produce greater severity of subacute withdrawal symptoms than BUP-NX during the first month after randomization, but will be equivalent to BUP-NX in months 2 to 6
 
Significance/Rationale: Low-grade withdrawal-like symptoms (dubbed “naltrexone flu” by the Columbia group, and consisting typically of insomnia, fatigue, and anorexia, though not drug craving) have been observed in some patients in the 1 to 4 weeks after naltrexone initiation, resolving gradually. Further characterization of this syndrome would be important for developing treatment guidelines.

Problems related to drug abuse (ASI-Lite and EQ-5D)	
XR-NTX will be superior to BUP-NX
 
Significance/Rationale: Greater opioid and non-opioid abstinence on XR-NTX will result in fewer problems associated with active drug abuse.

Table 1: Protocol Secondary Outcomes and Hypotheses	
Outcomes	Hypotheses
HIV risk behavior over time (RAB and other HIV risk measures)	XR-NTX and BUP-NX will be equivalent Significance/Rationale: The opioid-dependent population is at high risk for HIV, both from injection drug use and from unsafe sexual practices. Effective treatment for the opioid dependence may reduce HIV risk behavior. Given the high morbidity and mortality associated with HIV, a comparative advantage of one or the other of these treatments would be valuable to examine.
Cognitive function (Trails Making Test Parts A and B, Stroop)	XR-NTX and BUP-NX will be equivalent Significance/Rationale: Some providers and policy-makers are concerned that patients maintained on BUP-NX will have opioid-agonist-related cognitive impairment.

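### At scheduled weekly visits, listed non-serious withdrawal symptoms can be recorded as AEs at 0 of 4 visits in weeks 1-4 but 15 of 20 later, which can pull the between-arm AE test for withdrawal toward zero

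*SAP*

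**What the plan says.** **AE rule.** SAP 7.4.1 (with the same rule in Protocol 11.2.7, 13.6.4 and Appendix A) starts from this: "Events captured on study specific forms (INA, SOWS, HAM-D) will not be recorded separately as an AE, unless they meet the SAE definition". It adds: "Withdrawal symptoms not captured by the SOWS or HAM-D should be reported as an AE". A spontaneously reported withdrawal symptom then reaches the AE form in either of two situations. The first is "withdrawal symptoms reported at visits without scheduled specific structured questionnaires (SOWS, HAM-D"). The second is "withdrawal symptoms not listed in the specific structured questionnaires (SOWS, HAM-D) reported at any visit".

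**Scale schedule.** Protocol 11.4.6 gives the SOWS at baseline, at induction, "weekly during the first month after randomization, and at weeks 8, 12, 16, and 20", and then at week 24/EOT and follow-up. SAP 7.3 states: "The HAM-D is completed at screening, at weeks 1, 2, 3, 4, 8, 12, 16 and 20", and then at week 24/EOT and each follow-up.

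**Test.** SAP 7.4.1 says "The incidence of adverse events and serious adverse events by" type is compared between arms, by a Fisher mid-p or chi-square test.

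**Expectation.** SAP 2.2, Table 1, states: "XR-NTX will produce greater severity of subacute withdrawal symptoms than BUP-NX during the first month after randomization". It predicts equivalence in months 2 to 6. The same table predicts equivalent AE rates overall.

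**Separate reporting.** SAP 5.5.5 names the HAM-D and SOWS as the measures of subacute withdrawal. Tables 25, 26 and 47 summarise them by arm.

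**The concern.** Whether the same listed, non-serious symptom becomes an AE depends on the visit at which it is mentioned. The visits closed to it include every scheduled weekly visit in the one month when the plan expects the arms to differ. The resulting counts then enter a stated between-arm test.

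If the month-1 hypothesis is right, the AE comparison for withdrawal under-records the difference it ought to show, and so leans toward the plan's expectation of equivalent AE rates. The footnotes to the shells of Tables 33 and 35 explain treatment emergence only, so a reader of those tables would not know that capture changes by week. At stake is how a tested safety comparison is read. The primary outcome is not affected.

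**Working it through.** The plan states no figure for this point, so there is nothing to reproduce. The check crosses two calendars and then asks what follows.

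**Step 1: visits with a scale.** SOWS and HAM-D share weeks 1, 2, 3, 4, 8, 12, 16, 20 and 24 (Protocol 11.4.5 and 11.4.6; SAP 7.3). A visit is open if neither scale is scheduled.

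| Scheduled weekly visits | Total | With both scales | Open to a listed, non-serious symptom |
|---|---|---|---|
| Weeks 1-4 | 4 | 4 | 0 |
| Weeks 5-24 | 20 | 5 (8, 12, 16, 20, 24) | 20 - 5 = 15 |
| Weeks 1-24 | 24 | 9 | 24 - 9 = 15 |

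**Step 2: visits with active AE questioning.** Clinicians ask about AEs at medical management visits. Protocol 8.5 puts these at weeks 0-4, 6, 8, 10, 12, 14, 16, 20 and 24, which is 12 visits in weeks 1-24. Nine carry the scales, leaving 12 - 9 = 3 open: weeks 6, 10 and 14. The SOWS is also scheduled at the induction visit.

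**Step 3: what can still be recorded in weeks 1-4.** Three routes remain: symptoms not listed on the scales (second situation of the rule), events meeting the SAE definition, and reports at as-needed visits (Protocol 8.5.3), which carry no scheduled scale.

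**Step 4: direction if the plan's hypothesis holds.** Let b and x be the month-1 proportions with a listed, non-serious symptom on BUP-NX and XR-NTX. Let l be the later proportion, equal in both arms as Table 1 predicts, and take the two periods as independent. With every symptom counted, the difference is

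[1 - (1 - x)(1 - l)] - [1 - (1 - b)(1 - l)] = (x - b)(1 - l).

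If only later symptoms count, it is l - l = 0. The documents give no rates. The values below are assumptions that show a range, with l from 5% to 20%; power is for a two-sided 5% test with 300 per arm.

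| b vs x (assumed) | Difference, all counted | Power | Difference, later only |
|---|---|---|---|
| 10% vs 15% | 4.0 to 4.75 points | 19% to 34% | 0 |
| 10% vs 20% | 8.0 to 9.5 points | 56% to 84% | 0 |
| 10% vs 30% | 16 to 19 points | 98% or more | 0 |

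The zero is a limiting case, because the routes in step 3 let some month-1 events through. The 300 per arm is the projected number randomized, whereas Tables 33 and 35 count events only in inducted participants.

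**Step 5: a complication.** The scale calendar runs from randomization. Treatment emergence starts at induction, which may occur as late as week 22. A participant inducted after week 4 meets open visits soon after starting drug, so early post-induction symptoms can be recorded. SAP 3.2 expects induction to take longer on XR-NTX, so this works partly against the attenuation in step 4.

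**The case against.** The strongest defence is that the rule is deliberate. It avoids recording the same symptom twice, and withdrawal has its own secondary outcome with its own month-1 hypothesis, tabulated by arm in Tables 25, 26 and 47. No data are lost, and the plan already looks at withdrawal through the scales. That stands as far as it goes. It does not repair the AE test, which still uses counts whose capture changes by week.

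Three stronger readings are tempting, and the documents do not support them:

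- A reader might infer that no withdrawal symptom can be an AE in weeks 1-4. The rule's second situation, the SAE exception and as-needed visits all contradict that.
- A reader might infer that the AE contrast is reversed in favour of XR-NTX. That needs a later excess on BUP-NX, whereas Table 1 predicts equivalence in months 2 to 6. On the plan's own terms the pull is toward zero.
- A reader might infer that whole rows of Table 35, such as Insomnia, Vomiting or Hyperhidrosis, omit weeks 1-4. The exclusion applies to symptoms taken to be withdrawal, not to preferred terms, and the product labels list insomnia and vomiting as adverse events of both drugs. The SOWS items are not reproduced in the documents, so which terms they cover cannot be confirmed.

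For the same reason, removing every symptom that appears on the scales from AE testing would be too broad. It would discard valid comparisons of ordinary drug reactions.

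**Conclusion.** The point holds in limited form, as a cheap improvement. The visit counts (0 of 4 against 15 of 20, and medical management weeks 6, 10 and 14 only) follow directly from the schedules and rest on no assumption. That the between-arm AE test for withdrawal can be pulled toward zero depends on the plan's own hypothesis of more withdrawal on XR-NTX in month 1 and equivalence later. The size cannot be computed without symptom rates; the differences in the working are illustrations, not estimates. Late induction makes the direction less certain and means that weeks 1-4 after randomization are not the same as the first month on drug.

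**What to change.** Leave the AE collection rule as it is and change SAP 7.4.1 and its tables:

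1. Report AEs recorded as withdrawal (preferred term Drug withdrawal syndrome, plus AEs the clinician recorded as withdrawal symptoms) descriptively, without a between-arm test.
2. Show the any-AE and related-AE rows of Tables 33 and 35 with and without these events.
3. Keep testing insomnia, vomiting and other terms that were not recorded as withdrawal.
4. Footnote both tables: listed, non-serious withdrawal symptoms are recorded as AEs only at visits without a scheduled SOWS or HAM-D, so the tables should be read with Tables 25, 26 and 47.
5. Base the between-arm withdrawal comparison on SOWS and HAM-D scores at the common weeks (1-4, 8, 12, 16, 20, 24), and say so in SAP 5.5.5, which at present names no specific model and relies on the general text of 5.5. Keep the induction SOWS descriptive: it is given three times on XR-NTX and twice on BUP-NX, at times that vary by participant.

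The cost is SAP wording and one extra version of two tables, with no new data. The downside is that there would be no AE-based test of withdrawal.
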